**Programming notes:**

ADA Evaluable Patients are defined as patients with non-missing ADA status (Either Positive or Negative), ADA status is in the ADAB dataset provided by the MSA team.

## **Output 4.17 Laboratory Tests and Change from Baseline by Visit (LBT01)**

Protocol: GB41149

Analysis Population: Safety-evaluable population

Parameter: <parameter>					
Visit			Placebo (N = XXX)	MTPS9579A Active (N = XXX)	All Patients (N = XXX)
Baseline	Value at Visit	n	XXX	XXX	XXX
		Mean (SD)	XXXX (XXX)	XXXX (XXX)	XXXX (XXX)
		Median	XXXX	XXXX	XXXX
		Min - Max	XXX - XXXX	XXX - XXXX	XXX - XXXX
Day 22	Value at Visit	n	XXX	XXX	XXX
		Mean (SD)	XXXX (XXX)	XXXX (XXX)	XXXX (XXX)
		Median	XXXX	XXXX	XXXX
		Min - Max	XXX - XXXX	XXX - XXXX	XXX - XXXX
	Change from Baseline	n	XXX	XXX	XXX
		Mean (SD)	XXXX (XXX)	XXXX (XXX)	XXXX (XXX)
		Median	XXXX	XXXX	XXXX
		Min - Max	XXX - XXXX	XXX - XXXX	XXX - XXXX
	Percent Change from Baseline	n	XXX	XXX	XXX
		Mean (SD)	XX.X (XX.X)	XX.X (XX.X)	XX.X (XX.X)
		Median	XX.X (XX.X)	XX.X (XX.X)	XX.X (XX.X)
		Min - Max	XX.X (XX.X)	XX.X (XX.X)	XX.X (XX.X)
...					

## Output 4.18 Laboratory Test Results with Highest WHO Grade Post-Baseline (LBT07)

Protocol: GB41149

Analysis Population: Double-Blind Treatment Period; Safety-evaluable population (PHASE2\_SE)

Laboratory Test Direction of Abnormality	Highest WHO Grade	Placebo (N = XXX)	MTPS9579A Active (N = XXX)	All Patients (N = XXX)
Absolute neutrophil count	n	nn	nn	nn
Low	1	nn (xx.x  %)	nn (xx.x%)	nn (xx.x%)
	2	nn (xx.x%)	nn (xx.x%)	nn (xx.x%)
	3	nn (xx.x%)	nn (xx.x%)	nn (xx.x%)
	4	nn (xx.x%)	nn (xx.x%)	nn (xx.x%)
	Any	nn (xx.x  %)	nn (xx.x%)	nn (xx.x%)
Alkaline phosphatase	n	nn	nn	nn
High	1	nn (xx.x%)	nn (xx.x%)	nn (xx.x%)
	2	nn (xx.x%)	nn (xx.x%)	nn (xx.x%)
	3	nn (xx.x%)	nn (xx.x%)	nn (xx.x%)
	4	nn (xx.x%)	nn (xx.x%)	nn (xx.x%)
	Any	nn (xx.x%)	nn (xx.x%)	nn (xx.x%)
...				

## Output 4.19 Laboratory Test Results with Highest WHO Grade at Any Time (LBT08)

Protocol: GB41149

Analysis Population: Safety-evaluable population

[Similar to output 4.18]

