2.2 SAFETY OBJECTIVE

The safety objective for this study is to evaluate the safety of MTPS9579A compared with placebo on the basis of the following endpoints:

- Incidence and severity of adverse events, with severity determined according to the WHO Toxicity Grading Scale
- Change from randomization visit in physical examination findings
- Change from randomization visit in vital signs
- Change from randomization visit in ECG parameters
- Change from randomization visit in clinical laboratory results

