## **Output 4.22 Vital Sign Parameters outside Normal Limits Among Patients without Abnormality at Baseline (VST02\_2)**

Protocol: GB41149

Analysis Population: Safety-evaluable population

[Similar to output 4.21]

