## Output 4.36 Listing of Laboratory Abnormalities (including WHO grade) (LBL02A)

Protocol: GB41149

Analysis Population: Safety-evaluable population

TREATMENT: <Treatment>

---

Lab Test (Unit)	Center / Patient ID	Study Day	Cycle	Date	Days Since Last Dose of Study Drug	Result	Lab Normal Range	WHO Grade
<Lab Test> (<unit>)								
	xxxx/xxx	xx	xx	ddMMYY	xx	xx	XX-XX	xx
	xxxx/xxx	xx	xx	ddMMYY	xx	xx	XX-XX	xx
	xxxx/xxx	xx	xx	ddMMYY	xx	xx	XX-XX	xx
	xxxx/xxx	xx	xx	ddMMYY	xx	xx	XX-XX	xx
	xxxx/xxx	xx	xx	ddMMYY	xx	xx	XX-XX	xx
	xxxx/xxx	xx	xx	ddMMYY	xx	xx	XX-XX	xx

---

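### No laboratory table counts patients whose WHO grade is new or worse than at baseline: Output 4.18 ignores baseline grade, and Output 4.19, as titled, also takes in pre-drug values

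*SAP*

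**What the plan says.** The SAP has four laboratory outputs.

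- **Output 4.17**, "Laboratory Tests and Change from Baseline by Visit (LBT01": number of patients, mean, SD, median and range of the value, change and percent change at each visit. It has no patient counts by grade.
- **Output 4.18**, "Laboratory Test Results with Highest WHO Grade Post-Baseline (LBT07": for each test and direction, patients at highest grade 1, 2, 3, 4 and Any. Its scope is "Analysis Population: Double-Blind Treatment Period; Safety-evaluable population". It has no row, column or condition for baseline grade.
- **Output 4.19**, "Laboratory Test Results with Highest WHO Grade at Any Time (LBT08": the layout instruction is "Similar to output 4.18". The population is safety-evaluable, without the double-blind restriction of Output 4.18.
- **Output 4.36**, "Listing of Laboratory Abnormalities (including WHO grade) (LBL02A": a patient-level listing.

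For vital signs, Output 4.21 counts abnormalities whatever the baseline status, and Output 4.22 counts those "outside Normal Limits Among Patients without Abnormality at Baseline". Outputs 4.24 and 4.25 do the same for ECG.

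The SAP's Definition of Baseline section sets laboratory baseline at Week 2, using Screening for parameters with no Week 2 record. Among the safety endpoints in Protocol Section 2.2 is "Change from randomization visit in clinical laboratory results".

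**The concern.** A count by worst grade is read as a count of what happened on treatment. In Output 4.18, a patient who enters at Grade 1 and stays there is counted the same way as one who was normal and became Grade 1. In Output 4.19, a patient abnormal only at screening, and normal ever after, would appear as abnormal in the MTPS9579A column.

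Two consequences follow. If persisting abnormalities are equally common in both arms, they add the same background to each and shrink a real difference in new abnormalities. If they are unequal by chance, which is easy with 65 and 69 patients, the imbalance can look like a drug effect.

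The SAP handles this for vital signs and ECG by adding a second table conditioned on baseline. For laboratory data the second table goes the other way and widens the time window.

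**Working it through.** The documents state no figure for this point, so there is none to reproduce. There are two checks: whether the planned tables can yield the missing count, and how much difference it could make.

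**1. Can Outputs 4.18 and 4.19 together give the number new or worse?**

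Take one test in an arm of 69 (the MTPS9579A safety-evaluable count in SAP Output 1.1) and three constructed datasets. In each, 10 patients are as described and the other 59 are normal throughout.

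| Dataset | 10 patients (baseline → worst post-baseline) | 4.18 Any | 4.19 Any | New or worse |
|---|---|---|---|---|
| A | Grade 1 → Grade 1 | 10 | 10 | 0 |
| B | Normal → Grade 1 | 10 | 10 | 10 |
| C | Grade 1 → normal | 0 | 10 | 0 |

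A and B give identical entries in both tables, yet the number new or worse is 0 in one and 10 in the other. The two tables together cannot supply the count, and this needs no assumed rates. C shows what Output 4.19 adds under its title: 10 patients abnormal only before double-blind drug.

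**2. How large could the dilution be?**

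Inputs from the documents: 65 placebo and 69 MTPS9579A patients (SAP Output 1.1; 65 + 69 = 134).

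Inputs assumed, because the documents give none: new-onset risk of 5% on placebo and 15% on active among patients normal at baseline; a baseline abnormality prevalence b that is equal in both arms; and persistence of every baseline abnormality after baseline.

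Formulas:

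- Any-row rate in Output 4.18 = b + (1 − b) × new-onset risk.
- z = difference in rates / √[p₀(1 − p₀)/n₀ + p₁(1 − p₁)/n₁]. For Output 4.18, n₀ = 65 and n₁ = 69. For new abnormalities only, n₀ = 65(1 − b) and n₁ = 69(1 − b).
- Share of information kept = (z for 4.18 / z for new only)².

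Worked at b = 20%:

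- Placebo: 0.20 + 0.80 × 0.05 = 0.24. Active: 0.20 + 0.80 × 0.15 = 0.32.
- z for 4.18 = 0.08 / √(0.24 × 0.76/65 + 0.32 × 0.68/69) = 1.04.
- z for new only = 0.10 / √(0.05 × 0.95/52 + 0.15 × 0.85/55.2) = 1.76.
- Share kept = (1.036/1.761)² = 0.35.

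| Baseline prevalence b | 4.18 Any, placebo vs active | z for 4.18 | z for new only | Information kept |
|---|---|---|---|---|
| 2% | 6.9% vs 16.7% | 1.79 | 1.95 | 84% |
| 5% | 9.8% vs 19.3% | 1.58 | 1.92 | 68% |
| 10% | 14.5% vs 23.5% | 1.34 | 1.87 | 51% |
| 20% | 24.0% vs 32.0% | 1.04 | 1.76 | 35% |
| 30% | 33.5% vs 40.5% | 0.84 | 1.65 | 26% |

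The z-values only measure how visible the contrast is. The plan specifies no test on laboratory counts.

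**The case against.** **The protocol is met.** A reader might infer that the laboratory endpoint goes unreported. It does not. Protocol Section 2.2 asks for change from the randomization visit, Section 6.5 asks for descriptive statistics, and Output 4.17 gives both by arm. Its baseline row also helps to show an imbalance at entry. This stands.

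**Important abnormalities are captured elsewhere.** A reader might infer that laboratory toxicity would go unseen. Under Protocol Section 5.3.5.5, abnormalities that cause symptoms, change treatment, need intervention or are clinically significant must be reported as adverse events. They then enter Outputs 4.7 and 4.14. Laboratory patterns meeting Hy's Law are adverse events of special interest, with their own summary in Output 4.15. This largely stands. What stays uncounted is mainly grade changes without symptoms or action, and Output 4.36 would yield those only by hand.

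**Output 4.18 excludes pre-drug values.** It is post-baseline and limited to the double-blind period, so a reader who infers that both tables mix in pre-drug data is wrong. Only Output 4.19 can do so, and its title says as much openly. This stands. The fault in Output 4.18 is narrower: it does not separate a grade carried over from baseline from one that arose on treatment.

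**The rules are inferred from silence.** The outputs are template mock-ups, the SAP does not define any time, and two superscript markers in the Output 4.18 shell have no visible footnote. A counting rule may exist that is not shown. That is a fair caution, but no visible text contains a baseline condition.

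**The Any row is the worst case.** A move from Grade 1 to Grade 3 still shows in the Grade 3 row, and Grade 1 background barely affects rows 3 and 4. WHO Grade 1 for ALT, AST and ALP starts at 1.25 × ULN, and abnormalities judged to preclude safe participation are excluded, so baseline prevalence may be low for many tests. This stands, and is why the calculation includes low prevalences.

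**Conclusion.** The weakness is real and modest. As printed, none of Outputs 4.17, 4.18, 4.19 and 4.36 counts patients whose laboratory grade is new or worse than baseline, and Outputs 4.18 and 4.19 cannot be combined to give that count. The SAP provides a baseline-conditioned table for vital signs and ECG but not for laboratory tests.

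The size depends on assumption. With new-onset risks of 5% and 15% and full persistence, the Any row keeps about 68% of the information at 5% baseline prevalence, 35% at 20% and 26% at 30%. The documents support no single one of these figures, and a reader should not take any of them as this trial's expected loss. The direction is firmer: persisting abnormalities equally common in both arms dilute the contrast.

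That Output 4.19 takes in pre-drug values rests on its title and the absent period restriction. It is the natural reading, not a stated rule.

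**What to change.** Keep Output 4.18 as it is. It is the laboratory counterpart of Outputs 4.21 and 4.24, which count abnormalities whatever the baseline status.

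Replace Output 4.19 with a table, by arm and test, of baseline WHO grade against worst post-baseline WHO grade in the double-blind period. A simpler alternative is a count of patients whose worst post-baseline grade exceeds their baseline grade. Either form counts both new and worsened abnormalities and lets pre-drug values enter only as baseline. A straight copy of Output 4.22, limited to patients without the abnormality at baseline, would be weaker here because it omits patients who start abnormal and get worse.

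The cost is that the any-time table is lost and one table is reprogrammed. No new data are needed: the laboratory baseline is already derived in ADLB, and Output 4.19 as titled would already require grades for pre-drug values.

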## Output 4.20 Vital Signs Change from Baseline by Visit (VST01)

Protocol: GB41149

Analysis Population: Safety-evaluable population

<Parameter>

Placebo (N=nnn)	MTPS9579A Active (N=nnn)	All Patients (N=nnn)
--------------------	-----------------------------	-------------------------

Visit	Value at Visit	Change from Baseline	Value at Visit	Change from Baseline	Value at Visit	Change from Baseline
Baseline						
N	nnn		nnn		nnn	
Mean (SD)	xx.x (xx.x)		xx.x (xx.x)		xx.x (xx.x)	
Median	xx.x		xx.x		xx.x	
Min-max	xx.X-xx.X		xx.X-xx.X		xx.X-xx.X	
Day XX						
n	nnn	nnn	nnn	nnn	nnn	nnn
Mean (SD)	xx.x (xx.x)	xx.x (xx.x)	xx.x (xx.x)	xx.x (xx.x)	xx.x (xx.x)	xx.x (xx.x)
Median	xx.x	xx.x	xx.x	xx.x	xx.x	xx.x
Min-max	xx.X-xx.X	xx.X-xx.X	xx.X-xx.X	xx.X-xx.X	xx.X-xx.X	xx.X-xx.X
Day XX						
n	nnn	nnn	nnn	nnn	nnn	Nnn
Mean (SD)	xx.x (xx.x)	xx.x (xx.x)	xx.x (xx.x)	xx.x (xx.x)	xx.x (xx.x)	xx.x (xx.x)
Median	xx.x	xx.x	xx.x	xx.x	xx.x	xx.x
Min-max	xx.X-xx.X	xx.X-xx.X	xx.X-xx.X	xx.X-xx.X	xx.X-xx.X	xx.X-xx.X
...						

## Output 4.21 Vital Sign Parameters outside Normal Limits Regardless of Abnormality at Baseline (VST02\_1)

Protocol: GB41149

Analysis Population: Safety-evaluable population

Assessment	Direction of Abnormality	Placebo (N=nnn)	MTPS9579A Active (N=nnn)	All Patients (N=nnn)
Diastolic Blood Pressure	Low	nn/nnn (xx.x%)	nn/nnn (xx.x%)	nn/nnn (xx.x%)
	High	nn/nnn (xx.x%)	nn/nnn (xx.x%)	nn/nnn (xx.x%)

Systolic Blood Pressure	Low	nn/nnn (xx.x%)	nn/nnn (xx.x%)	nn/nnn (xx.x%)
Heart Rate	etc.	nn/nnn (xx.x%)	nn/nnn (xx.x%)	nn/nnn (xx.x%)
Temperature		nn/nnn (xx.x%)	nn/nnn (xx.x%)	nn/nnn (xx.x%)
...				

## **Output 4.22 Vital Sign Parameters outside Normal Limits Among Patients without Abnormality at Baseline (VST02\_2)**

Protocol: GB41149

Analysis Population: Safety-evaluable population

[Similar to output 4.21]

## **Output 4.23 ECG Parameters Change from Baseline by Visit (EGT01)**

Protocol: GB41149

Analysis Population: Safety-evaluable population

[Similar to output 4.20]

## **Output 4.24 ECG Parameters outside Normal Limits Regardless of Abnormality at Baseline (EGT02\_1)**

Protocol: GB41149

Analysis Population: Safety-evaluable population

[Similar to output 4.21]

## **Output 4.25 ECG Parameters outside Normal Limits Among Patients without Abnormality at Baseline (EGT02\_2)**

Protocol: GB41149

Analysis Population: Safety-evaluable population

[Similar to output 4.21]

## Output 4.26 QTcF Actual Values and Change from Baseline by Visit (EGT05\_QTCAT)

Protocol: GB41149

Analysis Population: Safety-evaluable population

Visit / Category	Placebo (N=nnn)	MTPS9579A Active (N=nnn)	All Patients (N=nnn)
Baseline			
Value at Visit			
n	nnn	nnn	nnn
<=450 msec	nn (xx.x%)	nn (xx.x%)	nn (xx.x%)
>450 to <=480 msec	nn (xx.x%)	nn (xx.x%)	nn (xx.x%)
>480 to <=500 msec	nn (xx.x%)	nn (xx.x%)	nn (xx.x%)
>500 msec	nn (xx.x%)	nn (xx.x%)	nn (xx.x%)
Day 22			
Value at Visit			
n	nnn	nnn	nnn
<=450 msec	nn (xx.x%)	nn (xx.x%)	nn (xx.x%)
>450 to <=480 msec	nn (xx.x%)	nn (xx.x%)	nn (xx.x%)
>480 to <=500 msec	nn (xx.x%)	nn (xx.x%)	nn (xx.x%)
>500 msec	nn (xx.x%)	nn (xx.x%)	nn (xx.x%)
Change from Baseline			
n	nnn	nnn	nnn
<=30 msec	nn (xx.x%)	nn (xx.x%)	nn (xx.x%)
>30 to <=60 msec	nn (xx.x%)	nn (xx.x%)	nn (xx.x%)
>60 msec	nn (xx.x%)	nn (xx.x%)	nn (xx.x%)
...			

## Listings

### Output 4.27 Listing of Drug Administration (EXL01)

Protocol: GB41149

Analysis Population: Double-Blind Treatment Period; Safety-evaluable population (PHASE2\_SE)

Treatment: xxxx (N=xx)

Center/ Patient ID	Visit	Study Day From	Study Day To	Treatment	Dose	Unit	Frequency	Route
	Day 1	1	27	RO12345678	25	MG	QD	ORAL
	Day 28	28	55	RO12345678	25	MG	QD	ORAL
	Day 1	1	27	RO12345678	25	MG	QD	ORAL
	Day 1	1	27	RO12345678	25	MG	QD	ORAL
	Day 28	28	55	RO87654321	50	MG	QD	ORAL
	Day 1	1	27	RO12345678	25	MG	QD	ORAL
	Day 28	28	55	RO12345678	25	MG	QD	ORAL
	Day 1	1	27	RO12345678	25	MG	QD	ORAL
	Day 28	28	55	RO12345678	25	MG	QD	ORAL
	...							

## Output 4.28 Glossary of Concomitant Medication Class, Preferred Name, and Investigator-Specified Terms (CML02A\_GL)

Protocol: GB41149

Analysis Population: Double-Blind Treatment Period; Safety-evaluable population (PHASE2\_SE)

ATC Class Level 2	WHO Drug Preferred Name	Investigator-Specified Treatment Term
Class2 1		
	Preferred Name 1	Investigator Text 1
		Investigator Text 2
	Preferred Name 2	Investigator Text 1
		Investigator Text 2
Class2 2	Preferred Name 1	Investigator Text 1
		Investigator Text 2
	Preferred Name 2	Investigator Text 1

Preferred Name 1

Investigator Text 1

Preferred Name 2

Investigator Text 1

---

## Output 4.31 Glossary of Adverse Event Preferred Terms and Investigator-Specified Adverse Event Terms (AEL01\_NOLLT)

Protocol: GB41149

Analysis Population: Safety-evaluable population

MedDRA System Organ Class	MedDRA Preferred Term	Investigator-Specified Adverse Event Term
BLOOD AND LYMPHATIC SYSTEM DISORDERS	ANAEMIA NOS	ANAEMIA
		ANEMIA
	LEUCOCYTOSIS NOS	LEUKOCYTOSIS
	LEUCOPENIA NOS	LEUKOPENIA
	LYMPHADENOPATHY	NECROTIC LYMPH NODE
		SWOLLEN GLANDS IN THROAT
		SWOLLEN THROAT GLANDS
CARDIAC DISORDERS	NEUTROPENIA	NEUTROPENIA
	CARDIOMYOPATHY NOS	CARDIOMYOPATHY
	CONGESTIVE (DILATED) CARDIOMYOPATHY	DILATED CARDIOMYOPATHY
	PERICARDIAL HAEMORRHAGE	PROBABLE PERICARDIAL BLEED
	TACHYCARDIA NOS	TACHYCARDIA
...		

## Output 4.32 Listing of Adverse Events (AEL02\_ED)

Protocol: GB41149

### Analysis Population:

- (1) Placebo Run-in Period; Run-in safety-evaluable population (PERIOD1\_PEFL)
- (2) 48-Week Double-Blind Treatment Period and 12-Week Safety Follow-up Period; Safety-evaluable population (PERIOD2\_SE)
- (3) 3 patients that were administered saline by IV infusion without IP at week18 visit (DEVI)

Treatment: <Treatment>

Center/Patient ID	Study Day at Onset	Time from Last Dose to Onset	AE Duration in Days	Most Extreme Intensity	Cause d by Study Drug	Outcome (1)	Treatment for AE	Action Taken (2)
Adverse Event MedDRA Preferred Term	Age/Sex/Race	days hrs mins	Serious					
ANEAMIA NOS	xxx*	xxx xx xx	1**	No	Mild	Yes	2	No
APPETITE DECREASED	xxx	xxx xx xx	2	No	Moderate	No	3	No
DIARRHEA NOS	xxx	xxx xx xx	2**	No	Mild	No	3	No

(1) Outcome: 1 = fatal; 2 = not recovered/not resolved; 3 = recovered/resolved; 4 = recovered/resolved with sequelae; 5 = recovering/resolving; 6 = unknown.

(2) Action taken: 1 = dose increased; 2 = dose not changed; 3 = dose reduced; 4 = drug interrupted; 5 = drug withdrawn; 6 = not applicable; 7 = unknown.

\* Study day derived from imputed onset date

\*\* Duration derived from imputed onset date and/or end date

## Output 4.33 Listing of Serious Adverse Events (AEL03)

Protocol: GB41149

### Analysis Population:

- (1) Placebo Run-in Period; Run-in safety-evaluable population (PERIOD1\_PEFL)
- (2) 48-Week Double-Blind Treatment Period and 12-Week Safety Follow-up Period; Safety-evaluable population (PERIOD2\_SE)

## Output 4.34 Listing of Adverse Events Leading to Study Treatment Discontinuation (AEL02\_ED)

Protocol: GB41149

Analysis Population: 48-Week Double-Blind Treatment Period and 12-Week Safety Follow-up Period; Safety-evaluable population (PERIOD2\_SE)

[Similar to output 4.32]

## Output 4.35 Listing of Adverse Events Leading to Study Discontinuation (AEL02\_ED)

Protocol: GB41149

Analysis Population: 48-Week Double-Blind Treatment Period and 12-Week Safety Follow-up Period; Safety-evaluable population (PERIOD2\_SE)

[Similar to output 4.32]

## Output 4.36 Listing of Laboratory Abnormalities (including WHO grade) (LBL02A)

Protocol: GB41149

Analysis Population: Safety-evaluable population

TREATMENT: <Treatment>

---

Lab Test (Unit)	Center / Patient ID	Study Day	Cycle	Date	Days Since Last Dose of Study Drug	Result	Lab Normal Range	WHO Grade
<Lab Test> (<unit>)								
	xxxx/xxx	xx	xx	ddMMYY	xx	xx	XX-XX	xx
	xxxx/xxx	xx	xx	ddMMYY	xx	xx	XX-XX	xx
	xxxx/xxx	xx	xx	ddMMYY	xx	xx	XX-XX	xx
	xxxx/xxx	xx	xx	ddMMYY	xx	xx	XX-XX	xx
	xxxx/xxx	xx	xx	ddMMYY	xx	xx	XX-XX	xx
	xxxx/xxx	xx	xx	ddMMYY	xx	xx	XX-XX	xx

---

## Output 4.37 Listing of Vital Signs (VSL01)

Protocol: GB41149

Analysis Population: Safety-evaluable population

Treatment: <Treatment>

Center / Patient ID Age/Sex/Race Visit/Time Point	Standard Range:	Pulse Rate (beats/min)	Respiratory Rate (breaths/min)	Systolic Blood Pressure (mmHg)	Diastolic Blood Pressure (mmHg)	Temperature (C)
		(60-100)	(8-20)	(90-130)	(60-80)	(36.5-37.5)
██████████ M	Study Day	Result	Change from BL Result	Change from BL Result	Change from BL Result	Change from BL Result
Screening	xx	xx	xx	xx	xx	xx
Baseline	xx	xx / L	xx	xx	xx	xx
Day 1/ 1HR	xx	xx / L	xx	xx	xx	xx
Day 1/ 2HR	xx	xx	xx			
Day 2/ 24HR	xx	xx	xx			
xxxx/xx	xx	xx				
xxxx/xxxxx xx/xx/xxxxx						
xxxxx/xxx	xx	xx	xx	xx	xx	xx
xxxxx/xxx	xx	xx / H	xx	xx	xx	xx
	xx	xx / H	xx			
	xx	xx	xx			

Baseline is the patient's last observation prior to initiation of study drug. Abnormalities are flagged as high (H) or low (L) if outside the Roche standard reference range.

## Output 4.38 Listing of ECG Data (EGL01)

Protocol: GB41149

Analysis Population: Safety-evaluable population

[Similar to output 4.37]

## Section 5. Biomarker (PD) Analysis

The analyses of all PD endpoints will be based on the safety-evaluable population.

## Tables

Below 3 tables will be covered in the Safety Section: Output 4.17 Laboratory Tests and Change from Baseline by Visit (LBT01). So there is no need to duplicate those tables.

1. Nasosorption Results and Change from Baseline by Visit and Tests
2. Urea-normalized Nasosorption Results and Change from Baseline by Visit and Tests
3. Serum Results and Change from Baseline by Visit and Tests

## Graphs

### **Output 5.1 Mean Value of Active Tryptase Over Time in Nasosorption**

Protocol: GB41149

Analysis Population: Safety-evaluable population; Nasosorption results (NASO\_SE)

### **Output 5.2 Mean Value of Total Tryptase Over Time in Nasosorption**

Protocol: GB41149

Analysis Population: Safety-evaluable population; Nasosorption results (NASO\_SE)

### **Output 5.3 Mean Value of Active Tryptase Over Time in Nasosorption - Urea Normalized**

Protocol: GB41149

Analysis Population: Safety-evaluable population; Nasosorption results (NASO\_SE)

### **Output 5.4 Mean Value of Total Tryptase Over Time in Nasosorption - Urea Normalized**

Protocol: GB41149

Analysis Population: Safety-evaluable population; Nasosorption results (NASO\_SE)

### **Output 5.5 Mean Value of Total Tryptase Over Time in Serum**

Protocol: GB41149

Analysis Population: Safety-evaluable population; Nasosorption results (SERUM\_SE)

### **Output 5.6 Mean Percent Change From Baseline of Total Tryptase Over Time in Serum**

Protocol: GB41149

Analysis Population: Safety-evaluable population; Nasosorption results (SERUM\_SE)

### **Output 5.7 Mean Percent Change From Baseline of Active Tryptase Over Time in Nasosorption**

Protocol: GB41149

Analysis Population: Safety-evaluable population; Nasosorption results (NASO\_SE)

### **Output 5.8 Mean Percent Change From Baseline of Total Tryptase Over Time in Nasosorption**

Protocol: GB41149

Analysis Population: Safety-evaluable population; Nasosorption results (NASO\_SE)

## **Output 5.9 Mean Percent Change From Baseline of Active Tryptase Over Time in Nasosorption - Urea Normalized**

Protocol: GB41149

Analysis Population: Safety-evaluable population; Nasosorption results (NASO\_SE)

## **Output 5.10 Mean Percent Change From Baseline of Total Tryptase Over Time in Nasosorption - Urea Normalized**

Protocol: GB41149

Analysis Population: Safety-evaluable population; Nasosorption results (NASO\_SE)

## **Output 5.11 Mean Value of Urea Over Time in Nasosorption**

Protocol: GB41149

Analysis Population: Safety-evaluable population; Nasosorption results (NASO\_SE)

## **Output 5.12 Mean Value of Urea Over Time in Serum**

Protocol: GB41149

Analysis Population: Safety-evaluable population; Nasosorption results (SERUM\_SE)
